**Addendum:**

**Section 8.3 Missing Data Approaches.**

The primary outcome analysis will be conducted using the intention-to-treat principle, and imputation will be used to adjust for the presence of missing data on the week 8 CAPS-5 assessment. We will compare baseline measurements between those with and without week 8 CAPS-5 scores to assess whether the data appear to be missing at random. Multiple imputation (via PROC MI, SAS) will be used to impute missing CAPS-5 values at week 8 based on information collected at the baseline visit. Five replicates of the imputed dataset will be generated, analyzed as specified in section 8.5 of the SAP, and PROC MIANALYZE will be used to generate final estimates and uncertainty measures (e.g. treatment effects and corresponding standard errors).

Analysis of secondary outcomes will generally include available data such that no data obtained within the study assessments windows will be discarded and no imputation for missing data will be done. Because these analyses were conducted with mixed model approaches, they are analyzed in a manner that is consistent with both the ITT principle and the missing at random assumption.

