## **8. STATISTICAL / ANALYTICAL ISSUES**

### **8.1 Analysis Populations**

This study will have two analysis populations, and intention-to-treat (ITT) population and a per protocol (PP) population.

The primary analysis will be based on the intention-to-treat principle. All participants who were enrolled and randomly allocated to a treatment arm will be included in the analysis in the group to which they were randomized (not to which treatment they actually received). This approach ignores noncompliance, protocol deviations, withdrawal and lost-to-follow-ups. Analysis of the ITT population avoids overoptimistic estimates of the efficacy of an intervention resulting from the removal of non-compliers, accepting that protocol deviations occur in actual clinical practice (Heritier, Gebski, & Keech, 2003).

Analyses will be replicated on the per-protocol population. The per-protocol population will consist of those participants who strictly adhered to the protocol (i.e., will exclude participants that withdrew or were lost-to-follow-up prior to completion of the study, received treatment they were not randomized to, completed visits outside of the prespecified window, participants known to the intervening anesthesiologist, baseline CAPS < 10, screening to baseline interval >32 days, or any other protocol deviation). The per-protocol analysis provides an estimate of the true efficacy of an intervention (i.e., among those who completed the treatment as planned) (Ranganathan, Pramesh, & Aggarwal, 2016).

A sensitivity analysis also will be performed, excluding subjects with final CAPS scores obtained more than 12 weeks post initial intervention and assigning discordant interventions to the one actually delivered.

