## **8.3 Missing Data Approaches**

The primary analysis will be conducted using the available data without any statistical imputation for missing data for data lost to follow up or otherwise unavailable. Accordingly, it is assumed for the primary analyses that missing primary outcomes are missing completely at random. We will examine the proportion of missing primary outcome data to ensure that the missing rate is comparable across the two treatments.

Analysis of the secondary objectives will generally include available data such that no data obtained within the study assessments windows will be discarded and no imputation for missing data will be done.

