**Reason for addendum:**

This addendum to the statistical analysis plan (SAP) is to document the methods to determine if the missingness observed in CAPS-5 week 8 data is random, and to describe the methods to impute the missing week 8 CAPS-5 values and the approach used to produce the final analysis.

The rationale for imputation of missing data for the primary outcome under the intention to treat (ITT) principle is that when the randomization process is disrupted by dropout or missing data outcomes, bias may be introduced that compromises the results.

The changes were made to provide additional clarification of the results in response to questions from journal reviewers.

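### Addendum 2's baseline comparison cannot assess whether week 8 CAPS-5 data are missing at random, and no planned analysis lets missingness depend on the unseen score

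*SAP*

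**What the plan says.** Addendum 2 is marked as written after unblinding and in response to journal reviewers. Its stated reason is to "document the methods to determine if the missingness observed in CAPS-5 week 8 data is random" and to describe the imputation. Its Section 8.3 says the team will "compare baseline measurements between those with and without week 8 CAPS-5 scores to assess whether the data appear to be missing at random". It will then "impute missing CAPS-5 values at week 8 based on information collected at the baseline visit". On the analysis it says: "Five replicates of the imputed dataset will be generated, analyzed as specified in section 8.5 of the SAP", with pooling in PROC MIANALYZE. For secondary outcomes it calls the mixed models "consistent with both the ITT principle and the missing at random assumption".

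Section 8.3 in the body of the SAP uses available data without imputation and says "it is assumed for the primary analyses that missing primary outcomes are missing completely at random". It adds one check: "We will examine the proportion of missing primary outcome data to ensure that the missing rate is comparable across the two treatments".

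The other analyses of the primary outcome are:
- the per-protocol analysis (SAP 8.1), which removes participants lost to follow-up;
- a sensitivity analysis (SAP 8.1) "excluding subjects with final CAPS scores obtained more than 12 weeks post initial intervention" and analysing discordant cases by the intervention delivered;
- covariate models (SAP 8.6.1);
- the baseline-diagnosis subgroup (Addendum Section 8.5.1).

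**The concern.** MAR allows missingness to depend on anything observed, baseline included. A baseline difference between participants with and without a week 8 CAPS-5 is therefore evidence against MCAR and fully compatible with MAR. The absence of a difference does not show that missingness is unrelated to the week 8 score itself. Whichever way the comparison falls, it cannot support a statement that the data appear MAR.

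This matters because the addendum's own rationale is that missing outcomes may bias the result. Loss related to outcome is plausible here. Protocol 3.1 accepts that some participants may be inadvertently unblinded, and Protocol 7.2 that those who learn they had sham may react badly. If participants who did poorly tend to skip the final interview, imputation from baseline data will not recover their scores. Nothing in the plan would show how far the primary conclusion depends on that.

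**Working it through.** **1. Search for an MNAR analysis.** Of the analyses listed above, none changes what is assumed about an unseen week 8 score given the observed data. Neither document contains a delta-adjusted, tipping-point, reference-based, pattern-mixture or selection-model analysis.

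**2. Behaviour of the check (simulation).** There were 2,000 trials per scenario at 160:80. Assumptions: baseline SD 10, change SD 10, true effect zero, change generated independently of baseline, and five imputations from arm and baseline CAPS-5 pooled by Rubin's rules.
- *MNAR:* SGB-arm missingness depended on the unseen change (logit slope 0.1 to 0.2 per point). The baseline t-test rejected in 4.6% to 5.0% of trials, its nominal false-positive rate. Imputation gave a spurious SGB benefit of 0.5 to 1.0 point at 5% missing, 1.4 to 2.4 at 15% and 2.2 to 3.5 at 25%. It agreed with the available-data estimate to within 0.01 point.
- *MAR:* missingness depended on baseline CAPS-5 only, at 15% and 25% missing. The t-test rejected in 99% to 100% of trials, yet imputation was biased by no more than 0.08 point, with type I error about 5%.

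The bias sizes depend on these assumptions. If change were correlated with baseline, the t-test would sometimes reject under MNAR too, but it still could not say which mechanism was at work.

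**3. Size of a departure.** The plan states no figure to reproduce here. The effect is SGB minus sham in week 8 minus baseline CAPS-5, so negative favours SGB. If missing scores are worse than imputed by delta:
- SGB only: shift = +f(SGB) × delta, towards no benefit;
- sham only: shift = −f(sham) × delta, towards more benefit;
- both arms: shift = [f(SGB) − f(sham)] × delta, near zero when the missing rates are similar.

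Inputs: 160:80 (Protocol 6.1); 25% attrition as the upper planning case (Protocol 8.4); 10 points as meaningful change (SAP 8.5); CAPS-IV SD 25 (Protocol 8.3). The 10% and 15% rates, delta 5 and a CAPS-5 SD of 12 are assumptions.

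| SGB missing | delta 5 | delta 10 | Completers |
|---|---|---|---|
| 10% | 0.10 × 5 = 0.50 | 1.0 | 144:72 |
| 15% | 0.15 × 5 = 0.75 | 1.5 | 136:68 |
| 25% | 0.25 × 5 = 1.25 | 2.5 | 120:60 |

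In standard errors, with SE = SD × √(1/n1 + 1/n2), ignoring baseline adjustment, at delta 10:
- SD 12, completers: SE = 12 × √(1/144 + 1/72) = 1.73, then 1.78 and 1.90. Ratios 1.0/1.73 = 0.58, 1.5/1.78 = 0.84, 2.5/1.90 = 1.32.
- SD 25, all 160:80: SE = 25 × √(1/160 + 1/80) = 3.42. Ratios 0.29, 0.44, 0.73.
- SD 25, completers: SE = 25 × √(1/144 + 1/72) = 3.61, then 3.71 and 3.95. Ratios 0.28, 0.40, 0.63.

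The SGB arm's own mean change, which SAP 8.5 sets against 10 points, moves by the same f × delta.

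**The case against.** The best defence is that the plan is less exposed than it looks, and much of that stands.
- A reader might infer that no analysis varies the missing-data assumption. The documents do not support this. The SAP body states MCAR with available data and Addendum 2 uses multiple imputation, so two assumptions are on record, along with a comparison of missing rates by arm. What stands is narrower: none is an MNAR analysis. The two also give nearly the same estimate in the simulation, because the Section 8.5 model already conditions on baseline CAPS-5.
- A reader might infer that the check would mislead the analysis. Addendum 2 attaches no decision rule to it, imputation goes ahead whatever it shows, and the wording is hedged. It is useful for describing departures from MCAR and for choosing imputation variables. Rewording it changes no estimate.
- A reader might infer that the result is biased in favour of SGB. The documents do not show this. If those who believed they had sham are the ones who leave, the loss could be heavier in the sham arm and the plan could understate benefit.
- Protocol 8.4 calls 25% attrition unlikely, and a delta of 10 means that every missing SGB participant is a full meaningful change worse than imputed. Both are upper cases.

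The imputation also names only baseline information, although PCL-5 is collected at weeks 2, 4, 6 and 8. Using those scores would make MAR more plausible. It would not test MNAR.

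**Conclusion.** The point holds in this form: the baseline comparison speaks to MCAR only, and the plan contains no analysis of the primary outcome under MNAR. The first part is a matter of logic and rests on no assumed number.

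The possible size is modest to material. For unseen SGB scores 5 to 10 points worse than imputed, the effect moves by 0.5 to 1.0 point at 10% missing and by 1.25 to 2.5 points at 25%. At delta 10 and 10%, 15% and 25% missing, that is about 0.6, 0.8 and 1.3 standard errors with an assumed SD of 12 on completers. With the planning SD of 25 on all 160:80 it is about 0.3, 0.4 and 0.7. The SD of 25 belongs to the CAPS-IV, and the documents give neither a CAPS-5 SD nor an observed missing rate. The direction is open. The documents do not show that the primary conclusion is wrong, only that its dependence on the missing-data assumption has not been examined for MNAR. The change should be made; the analysis plan is otherwise usable.

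**What to change.** 1. In Addendum 2, in both the reason and Section 8.3, describe the baseline comparison as a check of departures from MCAR among participants with and without a week 8 CAPS-5. Remove the statement that it assesses MAR.
2. Add a delta-adjusted multiple imputation of week 8 CAPS-5, labelled post hoc because Addendum 2 itself postdates unblinding. Use PROC MI with the MNAR statement and its ADJUST option. Worsen imputed scores by 0 to 10 points in SGB alone, in sham alone and in both arms. Fit the Section 8.5 model, and report the delta at which the primary conclusion changes, with the missing rate in each arm.

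Optionally, add the post-baseline PCL-5 scores to the imputation model. The cost is one extra table from existing data with a procedure already in use, plus a few lines of SAP text. If little is missing, the table will show that the result is robust.

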## PROTOCOL SYNOPSIS (CONTINUED)

---

Effectiveness Study Design:	Blinded, multi-center, randomized, sham-procedure-controlled
Number of Participants Planned:	240
Target Population:	active-duty service members
Duration of Study:	10 weeks
Diagnosis and Main Eligibility Criteria:	Participants with PCL-C score of 32 or higher All participants must have anticipated assignment to installation for at least 2 months and have been offered an A-level modality PTSD treatment (see section 4.1.2 for definition)
Study Procedures/Frequency:	CAPS-5 following screening (prior to week 0) and at week 8 Stellate ganglion block at weeks 0 and 2 PCL-5 and PCL-C at weeks 0, 2, 4, 6, and 8 M.I.N.I.-Plus Suicidality Items at screening and weeks 0, 2, 4, 6, and 8 K6 Scale at weeks 0, 2, 4, 6, and 8 SF-12, GAD-7, PHQ-9, AUDIT-C/AUDIT, pain scale at weeks 0, 4, and 8
Acceptability Objectives:	

• to assess participants' perceptions of stellate ganglion block in relation to other PTSD treatment options

• to inform communication with service members before, during, and after the procedure

Acceptability Study Design:	Qualitative study using focus groups, small group interviews, and individual interviews (both in person and over the phone).
Number of Participants Planned:	193
Target Population:	

• participants in effectiveness clinical trial and their spouses

• service members who have received SGB for PTSD symptoms at the participating study sites outside of the clinical trial and their spouse

• providers who have referred or could potentially refer patients for SGB for PTSD symptoms at the study sites

• clinicians who provide SGB for PTSD

Duration of Study:	no individual's participation will last more than 90 minutes
Main Eligibility Criteria:	

• participants in effectiveness clinical trial who received at least one intervention and initial follow-up within the prior three months

• service members who have received at least one SGB for PTSD symptoms at the study sites within the prior three months

• providers who have referred or could potentially refer service members for SGB for PTSD symptoms at the study sites

• providers who perform SGB for PTSD symptoms at the study sites

---

---

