### 6.3. Treatment and Treatment Assessments (Weeks 0 and 2)

The PCL-5, PCL-C, K6, and the M.I.N.I.-Plus Suicidality Items will be administered prior to the procedure at week 2.

Standard right-sided SGBs will be performed in accordance with this protocol ([Section 3.1](#)). On the day of the procedure, clinic nursing staff will perform standard nursing intake to include brief interim history, review of systems, vital signs, and placement of intravenous catheter. Females of child-bearing potential will have a urine pregnancy test. The treating physician will perform a targeted history and physical, paying attention to potential contraindications to SGB. At week 0, the physician will also give a brief explanation of the procedure as well as a review of risks and potential benefits, though these will have been described to them beforehand.

Injections will be performed under ultrasound visualization. The study medication will be either 7-10 mL 0.5% ropivacaine injected ventral to the right longus coli muscle (around and into the ventral fascia) and into the longus coli immediately dorsal to the presumed ventral fascia, at the level of the C6 anterior tubercle (landmarks for the stellate ganglion; active study medication) or 1-2 mL preservative free normal saline injected anterolateral to the anterior tubercle of C6 (sham procedure). The treating physician will access participant assignment (performed at RTI per protocol) via email from RTI's central office. The participant will not be informed which treatment he or she is receiving; for blinding purposes, the same type of syringes will be used for both injections. Similarly, the same number and types of syringes and other supplies should be placed on the sterile procedure table regardless to which intervention (SGB or sham) the participant has been randomized. The interaction of the treating physician with the participant will be scripted as much as possible (**Appendix 18**). Customary vital signs will be recorded. MEDCOM 40-54 dated Feb 09 provides "a standard process and procedure for

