#### **6.4. Post-Treatment Assessments (Weeks 4, 6, and 8)**

With the exception of the final CAPS-5, it is expected that these instruments will be completed by the participants on their own devices using a secure Web-based platform. For analytical purposes, each follow-up period will begin 2 days before the exact date of the follow-up and will end 11 days after the exact date of the follow-up. For example, the 2-week follow-up period will begin on day 12 and will end on day 25, the 4-week follow-up period will begin on day 26 and will end on day 38, etc. See **Appendix 19-1** and **19-2** for email communications, phone reminder script and contacting schedule.

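### Imputing the week-8 CAPS-5 from baseline-visit information alone cannot correct dropout that follows post-treatment symptoms, although PCL scores are scheduled at weeks 2 to 8

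*SAP*

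**What the plan says.** The main SAP, Section 8.3, made the primary analysis an available-case one: "The primary analysis will be conducted using the available data without any statistical imputation". It assumed data missing completely at random and planned to compare the missing proportion between arms.

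Addendum 2, dated after unblinding and written in response to journal reviewers, changes this. Its stated reason is that "when the randomization process is disrupted by dropout or missing data outcomes, bias may be introduced that compromises the results". The method is multiple imputation, which "will be used to impute missing CAPS-5 values at week 8 based on information collected at the baseline visit". The check on the mechanism is "We will compare baseline measurements between those with and without week 8 CAPS-5 scores". Then: "Five replicates of the imputed dataset will be generated, analyzed as specified in section 8.5 of the SAP". The addendum does not list the imputation variables or say whether treatment arm is among them.

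The Protocol Synopsis schedules "PCL-5 and PCL-C at weeks 0, 2, 4, 6, and 8". Protocol 6.3 places one of these between the two injections: "The PCL-5, PCL-C, K6, and the M.I.N.I.-Plus Suicidality Items will be administered prior to the procedure at week 2". For weeks 4 to 8, Protocol 6.4 says: "With the exception of the final CAPS-5, it is expected that these instruments will be completed by the participants on their own devices". The final CAPS-5 is a separate telephone interview (Protocol 6.4.1). No section brings the post-baseline PCL scores into the imputation.

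**The concern.** The purpose and the method do not match. Dropout by participants who do poorly after the procedure is a plausible source of the bias that the addendum names. Baseline data address it only as far as baseline predicts the post-treatment course, and the Section 8.5 model already adjusts for baseline CAPS-5. The missingness check has the same blind spot: a comparison of baseline values cannot show that people left because of what happened later.

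Better information may well be on file. A participant can complete the week-2 clinic PCL or the later online forms and still miss the telephone CAPS-5.

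At stake is how the imputed intention-to-treat result is read. It would look like a robustness check while, for this kind of dropout, adding almost nothing to the analysis it supplements. The direction of the remaining bias depends on which arm loses its poor responders, so it can shrink or inflate the effect.

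**Working it through.** **1. The plan's own design figures.** The plan gives no figure for this problem. The nearest are the powers in Protocol 8.3: 240 participants at 2:1 (160 and 80), SD 25, type I error 0.05.

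- SE = 25 × √(1/160 + 1/80) = 3.42
- 15 points: Φ(15/3.42 − 1.96) = Φ(2.42) = 0.992 (stated 0.99)
- 10 points: Φ(10/3.42 − 1.96) = Φ(0.96) = 0.832 (stated 0.83)

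Both reproduce, so the simulation uses 160 and 80. The SD of 25 belongs to the CAPS-IV and is not used below.

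**2. What the imputation can change.** The Section 8.5 model is

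change = β0 + β1·arm + β2·site + β3·baseline CAPS-5 + error.

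If the imputation model holds only those covariates, the missing values are drawn from that same regression fitted to the completers. The pooled β1 is then the available-case β1 plus simulation noise. A different answer needs a variable that predicts the missing score beyond these covariates. If dropout depends on a post-treatment PCL score P, the distribution required is that of the week-8 score given arm, site, baseline **and** P.

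**3. Simulation.** Assumed, not from the documents: true effect −5, residual SD 11, PCL–CAPS residual correlation 0.7. Dropout in the affected arm or arms:

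logit P(missing) = logit(base rate) + 1.0 × (week-6 PCL in SD units),

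with the base rate in any other arm. Five imputations, as in the addendum, each analysed with the Section 8.5 model. Mean estimates:

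| Base rate | Analysis | Both arms | Sham only | Active only |
|---|---|---|---|---|
| 20% | Available case | −4.56 | −3.34 | −6.32 |
| 20% | MI: baseline + arm | −4.56 | −3.34 | −6.31 |
| 20% | as above + baseline auxiliary (residual correlation 0.4) | −4.61 | −3.59 | −6.10 |
| 20% | MI with PCL | −4.96 | −5.02 | −4.98 |
| 20% | MI with PCL, half of those missing have none | −4.82 | −4.35 | not run |
| 10% | MI: baseline + arm | −4.77 | −3.97 | −5.73 |
| 10% | MI with PCL | −5.01 | −5.00 | −4.97 |
| 10% | MI with PCL, half of those missing have none | −4.96 | −4.56 | not run |

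The half-without-PCL rows use 1,500 replicates (Monte Carlo SE about 0.04); the others use 3,000 (about 0.03). The 20% base rate gives 21–24% missing.

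Bias of baseline-plus-arm MI (estimate minus −5):

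- 20%: +0.44 (both), +1.66 (sham), −1.31 (active)
- 10%: +0.23 (both), +1.03 (sham), −0.73 (active)

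For scale, the full-data SE is 11 × √(1/160 + 1/80) = 1.51. The both-arms bias is therefore 0.15 SE (0.23/1.51) to 0.29 SE (0.44/1.51). The sham-only bias at 20% is 1.10 SE (1.66/1.51).

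With the correlation lowered to 0.5 (20%), baseline MI gives −4.7 (both) and −3.8 (sham only); with the PCL, −5.0.

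**4. Other assumptions.** True effect −6, SD 12, baseline correlation 0.5, PCL–CAPS correlation given baseline 0.5 to 0.85, five imputations, 800 trials per scenario. Bias of baseline MI:

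| Dropout pattern | 10% | 25% |
|---|---|---|
| Poor responders leave active only | −0.4 to −0.7 | −1.0 to −1.7 |
| Poor responders leave sham only | +0.5 to +0.8 | +1.0 to +1.8 |
| Same pattern in both arms | +0.05 to +0.26 | +0.16 to +0.46 |

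Baseline MI stayed within 0.02 of available case throughout. With the PCL added, bias was within about 0.1, which is Monte Carlo error.

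**5. Arm in the imputation model.** If arm were omitted, the first set of assumptions gives −4.4 at 10% and −4.0 at 20%, even with data missing completely at random.

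**The case against.** The wording of the plan is not in dispute. The case against is about strength.

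- **Baseline may mean a rich set.** The week-0 visit collects PCL-5, PCL-C, K6, PHQ-9, GAD-7, SF-12, pain and medications. So the equality with available case, which assumes only the Section 8.5 covariates, may rest on too narrow a reading. This stands in part: the claim is properly about dropout beyond what baseline predicts. But the auxiliary run moved the estimate by at most 0.25 (−3.34 to −3.59). The baseline CAPS-5 is taken by telephone before week 0, so the words do not settle even whether it is included.
- **The remedy works by construction.** Dropout was generated from the score then added to the imputation. That is so, and the half-without-PCL rows show the cost. If people stop the online forms and the interview together, the gain approaches zero.
- **The larger figures need one-arm dropout.** This stands: with the same mechanism in both arms, the bias is a fraction of a standard error. Protocol 8.4 calls 25% attrition unlikely, and participants are meant to be blinded. However, Protocol 3.1 accepts that participants may recognise a block, and 7.2 that those who learn they had sham may react badly.
- **Related analyses exist.** The SAP compares missing rates between arms, and its PCL-5 mixed model uses all available post-baseline scores. Neither repairs the CAPS-5 result.
- **Arm omission is not shown.** Correct; that point is a request for clarification.
- **Any change comes after unblinding.** Also correct; it bears on labelling and reporting.

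**Conclusion.** The concern holds. Addendum 2 limits both the imputation and the missingness check to baseline, so dropout linked to post-treatment symptoms is left essentially where the available-case analysis left it, contrary to the addendum's own reason for imputing.

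The textual point is firm; the size is illustrative. Under the first set of assumptions the bias runs from about 0.2 to 0.4 CAPS-5 points when dropout acts alike in both arms, and from about 0.7 to 1.7 points, in either direction, when it acts in one arm only. The documents give neither the missing rate nor the number of non-completers with interim PCL scores. Adding the PCL makes missing at random more plausible. It does not cover dropout that depends on the unobserved CAPS-5 itself.

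**What to change.** In Addendum 2, Section 8.3:

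1. List the imputation variables and confirm that treatment arm is one of them.
2. Add an analysis that imputes week-8 CAPS-5 from arm (or separately by arm), site, baseline CAPS-5 and all available week 0 to 8 PCL-5 or PCL-C scores. The PCL enters the imputation only; the Section 8.5 analysis model is unchanged.
3. Compare participants with and without a week-8 CAPS-5 on interim PCL as well as baseline, by arm. Report how many of those missing have any interim PCL score.
4. Label the new analysis post hoc and report it beside the pre-specified available-case result and the baseline-only imputation, replacing neither.

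A delta-adjusted sensitivity analysis and more than five imputations are optional additions.

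The cost is one SAP paragraph and a few lines of PROC MI, with no new data collection. The drawbacks are one more post-unblinding analysis and little gain for early dropouts with no interim PCL.
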